2.2 Hypotheses and/or Estimations

- AMG 529 will be safe and well tolerated after single dose SC or IV administration in healthy subjects.
- AMG 529 PK profile following single dose SC administration will allow for determination of dose and frequency of administration in future multi-dose trials of AMG 529.

3. Study Overview

3.1 Study Design

This is a randomized, double-blind, placebo-controlled, ascending single-dose study in healthy subjects, which will be conducted at 1 to 3 sites in the United States.

Approximately 48 subjects will enroll in 1 of 6 dose cohorts (8 per cohort).

For cohorts 1, 2, 3, 4, and 5, eight (8) subjects will be randomized to receive AMG 529 or placebo SC in a 3:1 ratio at dose levels of 21, 70, 210, 420, and 700 mg, respectively.

In cohort 6, eight (8) subjects will receive AMG 529 or placebo IV in a 3:1 ratio at a dose level of 70 mg. The planned doses of AMG 529 are shown below:

Planned Treatment by Cohort

Cohort	Dose/Route	No. of Subjects		
		AMG 529	Placebo	Total
1	21 mg SC	6	2	8
2	70 mg SC	6	2	8
3	210 mg SC	6	2	8
4	420 mg SC	6	2	8
5	700 mg SC	6	2	8
6	70 mg IV	6	2	8

For all cohorts, the first 2 subjects (sentinel pair) will be randomized such that 1 subject will receive AMG 529 and 1 subject will receive placebo, and observed for at least 24 hours before the remaining subjects in the cohort are dosed, provided there are no safety or tolerability concerns as assessed by the principal investigator. Escalation to a higher dose cohort will only proceed when the previous dose regimen has been found to be safe and reasonably tolerated based on available safety and laboratory data through study day 15 for all subjects and upon unanimous decision at the Dose Level Review Meeting (DLRM). Enrollment can be initiated in cohort 5 and cohort 6 after the dose regimen in cohort 4 has been found to be safe and well tolerated. Cohort 6 will start enrollment after the completion of cohort 5 enrollment.

3.2 Sample Size

The sample size is based on practical considerations. Approximately 48 healthy subjects will enroll to participate in cohorts 1 through 6 of this study. With 6 subjects receiving AMG 529 in a cohort there is a 74% chance of detecting an adverse event with a true incidence of 20%. With 36 subjects receiving AMG 529 there is an 84% chance of detecting an adverse event with a true incidence of 5%.

4. Covariates and Subgroups

4.1 Planned Covariates

Baseline values may be used as a covariate in analyses. For any variable, unless otherwise defined, baseline is defined as the last assessment taken prior to the first administration of AMG 529 or placebo.

4.2 Subgroups

Not applicable.

5. Definitions

Age

Subject age at randomization will be determined using the age in years reported in the clinical database.

Baseline

For any variable, unless otherwise defined, baseline is the last assessment taken prior to the first investigational product administration.

ECG Analysis Value

On Day -1 baseline, three sets of triplicate ECGs will be collected ≥ 30 minutes apart and at other time-points single triplicate ECGs will be collected, approximately 60 seconds apart. The mean value of triplicate will be calculated and used in the analysis. If an ECG is missing within a triplicate, all available data will be averaged for that timepoint.

Baseline ECG

The baseline ECG is defined as the average of the mean of the triplicates at Day -1; the mean of values in a triplicate should be calculated before taking the mean of the triplicate averages.

Change from Baseline

Change from Baseline is the arithmetic difference between post-Baseline and Baseline.

End-of-Study

Primary Completion: the time when the last subject has completed the EOS visit as outlined in Section 7.1 of the Schedule of Assessments in the protocol.

End of Trial: the time when the last subject has completed either the EOS visit or the last safety follow-up visit.

The EOS for each cohort may be prolonged pending treatment- emergent data.

Definitions of the end of study for an individual and completion of the study as a whole are detailed in Section 3.5.1 of the protocol.

Enrollment Date

Enrollment date is defined as the randomization date.

Investigational Product

The term 'investigational product' is used in reference to AMG 529 or placebo.

Study Day

Post study day 1: study day= (date - date of Study Day 1) + 1 Study Day

Pre study day 1: study day= (date – date of Study Day 1)

Study Day 1

Study day 1 is defined as the first day of administration of the investigational product after enrollment. The day prior to Study Day 1 is considered Day -1.

Treatment-Emergent Adverse Event (TEAE)

A treatment-emergent adverse event is any adverse event starting on or after the first dose of investigational product, as determined by the flag indicating if the adverse event started prior to the first dose on the Adverse Events Summary CRF and up to end of study (EOS).

Fridericia-corrected QT Interval (QTcF)

The Fridericia correction will be calculated from the investigator reported QT (msec) and RR interval (msec), as follows: Fridericia-corrected QT Interval (QTcF)

$$QTcF = QT / (RR/1000)^{1/3}$$

6. Analysis Sets

For all analyses, subjects will be analyzed according to the dose and treatment they received, not the dose and treatment to which they were randomized.

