#### **End of Study (EOS)**

Subjects in cohorts 1 (21 mg SC), 2 (70 mg SC) and 6 (70 mg IV) will return to the research facility for an end-of-study (EOS) visit on day 30. Subjects in cohorts 3 (210 mg SC), 4 (420 mg SC) and 5 (700 mg SC) will return to the research facility for an EOS visit on day 57. This visit will complete the subjects' participation in this study. If there is a clinically significant clinical or laboratory abnormality in need of monitoring, subjects will be followed until resolution of the abnormality or until it is considered stable.

Blood samples will be collected at baseline and EOS as outlined in the Schedule of Assessments for the measurement of anti-AMG 529 antibodies. The measurement of anti-AMG 529 antibodies will be conducted on these samples only if there are unexpected PK findings or a safety signal in this study or future studies that warrants further investigation by characterizing drug immunogenicity. Samples testing positive may be further characterized for quantity/titer, isotype, affinity, and/or in vitro neutralizing activity. If the anti-AMG 529 antibody samples are analyzed, subjects who test positive for binding antibodies at the final scheduled study visit and have clinical sequelae that are considered potentially related to an anti-AMG 529 antibody response may also

be asked to return for additional follow-up testing. This testing should occur approximately every 3 months starting from when the site has been notified of the positive result, until: (1) antibodies are no longer detectable or (2) the subject has been followed for a period of at least 1 year ( $\pm$  4 weeks). More frequent testing (eg, every month), or testing for a longer period of time may be requested in the event of safety-related concerns. Follow-up testing will not be required where it is established that the subject did not receive AMG 529.

[figure not shown]

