### **7.2.4 End of Study Visit**

Subjects will return to the clinic for follow-up visits in accordance to the Schedule of Assessments ([Table 4](#) and [Table 5](#)) and be followed through the completion of the EOS procedures on day 30 for cohorts 1 (21 mg SC), 2 (70 mg SC) and 6 (70 mg IV) and day 57 for cohorts 3 (210 mg SC), 4 (420 mg SC) and 5 (700 mg SC). If an EOS test result demonstrates a clinically significant clinical or laboratory abnormality, the subject will be followed until resolution of the abnormality or until it is considered clinically stable by the investigator.

At the EOS visit, the following measures will be performed as per the Schedule of Assessments:

- Physical Examination
- Weight
- Triplicate 12-lead ECG
- Vital signs (eg, blood pressure, respiratory rate, heart rate, oral temperature)
- Safety laboratory assessments: clinical chemistry, hematology, coagulation, and urinalysis
- eGFR

- On-study lipid panel
- PK, biomarker (only for cohorts 1, 2 and 6), alkaline phosphatase isoenzymes (only for cohorts 1, 2 and 6) and anti-AMG 529 antibody sample collection
- Pregnancy test (female subjects only)
- Serious Adverse Event reporting
- Adverse Event reporting
- Documentation of all concomitant medications

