## **9.2 Safety Event Reporting Procedures**

### **9.2.1 Adverse Events**

#### **9.2.1.1 Reporting Procedures for Adverse Events That do not Meet Serious Criteria**

The investigator is responsible for ensuring that all adverse events observed by the investigator or reported by the subject that occur after first dose of investigational product (AMG 529 or placebo) through the End of Study are reported using the Event CRF.

The investigator must assign the following adverse event attributes:

- Adverse event diagnosis or syndrome(s), if known (if not known, signs or symptoms),
- Dates of onset and resolution (if resolved),
- Severity (and/or toxicity per protocol),
- Assessment of relatedness to IP (AMG 529 or placebo)
- Assessment of relatedness to any study-mandated activity/procedure
- Action taken.

Determination of the severity of adverse events will be as follows: grade 1 = mild (eg, asymptomatic or mild symptoms, clinical or diagnostic observations only, intervention not indicated, or does not interfere with activity); grade 2 = moderate (eg, minimal intervention indicated or interferes with activity); grade 3 = severe (eg, medically significant but not immediately life-threatening, prevents daily activity, or requires treatment); grade 4 = life-threatening (ie, refers to an event in which the subject was, in the view of the investigator, at risk of death at the time of the event); and grade 5 = fatal.

The investigator must assess whether the adverse event is possibly related to the administration of investigational product (AMG 529 or placebo). This relationship is indicated by a “yes” or “no” response to the question: Is there a reasonable possibility that the event may have been caused by the investigational product (AMG 529 or placebo)? Relatedness means that there are facts or reasons to support a relationship between investigational product and the event.

The investigator must assess whether the adverse event is possibly related to any study mandated activity (eg, administration of investigational product and/or study procedure, including screening procedures). This relationship is indicated by a “yes” or “no” response to the question: Is there a reasonable possibility that the event may have been caused by a study activity (eg, administration of investigational product and/or study procedure)?

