9.1 General Considerations

Descriptive statistics will be provided for selected demographics, safety, PK, and PD data. Data for subjects receiving placebo will be combined across all cohorts, except for adverse events where the combined SC cohorts will be summarized separately from the IV cohort. Descriptive statistics on continuous measurements will include means, medians, standard deviations, and ranges, while categorical data will be summarized using frequency counts and percentages. Data will be summarized by treatment group and at each time point when samples are collected. The number and percent of subjects reporting any treatment-emergent adverse events will be tabulated by system organ class and preferred term and will be further classified by relationship to treatment.

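### TEAEs are counted to Day 30 at 21 and 70 mg SC but to Day 57 at 210, 420 and 700 mg SC, so crude incidence is not like-for-like across that divide or against pooled SC placebo

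*SAP*

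**What the plan says.** **Counting window.** SAP Section 5 (Treatment-Emergent Adverse Event) includes any event that begins at or after dosing, identified by the flag for whether it "started prior to the first dose on the Adverse Events Summary CRF and up to end of study (EOS"). No number of days is fixed. Protocol 9.2.1.1 collects non-serious events over the same span: those that "occur after first dose of investigational product (AMG 529 or placebo) through the End of Study are reported using the Event CRF".

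**Length of follow-up.** Protocol 7.2.4 sets the last visit at "day 30 for cohorts 1 (21 mg SC), 2 (70 mg SC) and 6 (70 mg IV") and at "day 57 for cohorts 3 (210 mg SC), 4 (420 mg SC) and 5 (700 mg SC"). The synopsis agrees: the first group "will return to the research facility for an end-of-study (EOS) visit on day 30", and the second "will return to the research facility for an EOS visit on day 57". SAP Section 5 (End-of-Study) adds a further possibility: "The EOS for each cohort may be prolonged pending" treatment-emergent data.

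**Summary measure.** TEAE incidence is a primary endpoint (Protocol 10.1.1.1, SAP 2.1). SAP 9.1 and 9.6.2 report it as number and percent of subjects by treatment group. Placebo is pooled over all cohorts, "except for adverse events where the combined SC cohorts will be summarized separately from the IV cohort". With 2 placebo subjects per cohort, SC placebo is 10 subjects and IV placebo is 2.

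Neither document gives a common cut-off, a person-time rate or a time-to-event summary for adverse events.

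**The concern.** A crude percentage of subjects with at least one event grows with the time over which subjects are watched. Here that time changes between 70 and 210 mg SC, so follow-up and dose are confounded at that point. The pooled SC placebo mixes both lengths and matches no single SC dose group.

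No formal inference is planned for adverse events, so these percentages are the primary safety result. A reader who sets them side by side could see the higher doses doing worse than placebo, and the two lower SC doses doing better, when the drug has no effect.

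**Working it through.** **The plan's own figures.** SAP 3.2 gives the chance of seeing at least one event, 1 − (1 − p)^n:
- n = 6, p = 20%: 1 − 0.8^6 = 0.738, stated as 74%.
- n = 36, p = 5%: 1 − 0.95^36 = 0.842, stated as 84%.

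Both reproduce. Neither says over what period the true incidence applies, and the 36 comprise 18 subjects followed to Day 30 and 18 to Day 57.

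**Inputs from the documents.** EOS is Day 30 (cohorts 1, 2, 6) or Day 57 (cohorts 3, 4, 5), with 6 active and 2 placebo subjects per cohort. SC placebo is therefore 2 × 2 = 4 subjects to Day 30 and 3 × 2 = 6 to Day 57, a mean of (4 × 30 + 6 × 57)/10 = 46.2 days. The follow-up ratio is 57/30 = 1.9 (56/29 = 1.93 in elapsed days).

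**Assumption.** The documents give no background event rate, so the 30-day incidence p30 is varied. The drug is taken to be inert.

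**Constant background hazard.** p57 = 1 − (1 − p30)^1.9, and expected SC placebo incidence = (4 × p30 + 6 × p57)/10.

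| p30 (21, 70 mg SC) | p57 (210, 420, 700 mg SC) | Step | Pooled SC placebo |
|---|---|---|---|
| 5% | 9.3% | 4.3 points | 7.6% |
| 10% | 18.1% | 8.1 points | 14.9% |
| 20% | 34.6% | 14.6 points | 28.7% |
| 30% | 49.2% | 19.2 points | 41.5% |
| 40% | 62.1% | 22.1 points | 53.3% |

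At p30 = 30%, each lower-dose SC cohort expects about 1.8 of 6 active subjects with a TEAE and each higher-dose cohort about 3.0 of 6. Lower doses sit 11.5 points below placebo and higher doses 7.7 points above it.

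**Lower hazard after Day 30.** If the later hazard is a fraction f of the earlier one, p57 = 1 − (1 − p30)^(1 + f × 27/30). At p30 = 30%:
- f = 0.5: 40.4%, a step of 10.4 points.
- f = 0.25: 35.4%, a step of 5.4 points.
- f = 0: 30%, no step.

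**Front-loaded events.** If half the 30-day hazard falls in the first 6 days, the other half is spread over 24 days. Continuing that rate for 27 more days multiplies the cumulative hazard by 1 + 0.5 × 27/24 = 1.5625. Then 20% becomes 29.4%, and 40% becomes 55.0%.

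**What would be observed.** Take 12 active subjects at 21 or 70 mg SC and 18 at 210 to 700 mg SC, p30 = 30%, constant hazard and no drug effect. The higher-dose group shows the larger observed percentage with probability 0.84, and the lower-dose group with probability 0.12. With a common 30-day window these are 0.47 and 0.46.

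**Comparisons that are matched.** These are 21 versus 70 mg SC; 210, 420 and 700 mg SC among themselves; and IV active versus IV placebo. All SC active subjects combined would also match pooled SC placebo: (12 × 30 + 18 × 57)/30 = 46.2 days.

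**The case against.** The strongest reply is that longer follow-up at higher doses is deliberate. In a first-in-human antibody study with an anticipated half-life of 7 to 10 days (Protocol 2.5), reporting every event to EOS is a legitimate conservative choice that matches the collection period. That stands: the longer follow-up is not an error, and the to-EOS tables should not be demoted.

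Several stronger readings are also tempting, and the documents do not support them:
- *Incidence rises steadily with dose.* There are only two windows, so an inert drug gives one step, flat on either side.
- *Escalation is distorted.* Each scheduled review uses data through Day 15 for all subjects in the cohort (SAP 3.1).
- *Dose selection for the multi-dose trial is biased.* The stated hypothesis ties dose and frequency to the PK profile (SAP 2.2), not to crude TEAE incidence.
- *The counting window depends on outcome.* Prolonging EOS is only a possibility, and it is stated per cohort, so it would cover that cohort's placebo subjects too. It could still widen the gap between cohorts.

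There is partial mitigation. TEAEs are also classified by relationship to treatment, and blinded attribution should remove some late background events, though not all. Observation is densest early, with residency to Day 6 and only two scheduled visits after Day 30, which favours the smaller estimates. Onset dates are collected, so a Day 30 cut could be produced at any time. But a cut chosen after unblinding is weaker than one fixed in the SAP.

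**Conclusion.** The point holds as a gap in the analysis plan. Crude TEAE incidence is not comparable between the 21 and 70 mg SC groups and the 210, 420 and 700 mg SC groups, nor between any one SC dose and pooled SC placebo. If background events continue after Day 30, the direction is predictable: one upward step between 70 and 210 mg SC, with the lower doses below placebo and the higher doses above it.

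The design facts are certain; the size is not. It runs from zero with no events after Day 30, through about 5 points at a 30% 30-day rate with a quarter of the hazard later, to about 22 points at a 40% rate with constant hazard. All the rates are assumptions. The adverse event summaries are descriptive, so no error rate or power figure changes.

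**What to change.** Keep the full to-EOS TEAE tables as planned. Beside them, add to the SAP:
- a prespecified set of tables counting TEAEs with onset from first dose through Day 30 in every cohort and in placebo;
- subject-days and events per 100 subject-days over full follow-up, by treatment group;
- a statement that comparisons across SC doses and with pooled SC placebo rest on the common window;
- a statement that prolonging a cohort's EOS does not move the Day 30 window.

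The common window should carry the comparison because a rate per subject-day is fair only if the hazard is roughly constant. In the front-loaded case above, the full-follow-up rate in the 57-day cohorts would be 1.5625/1.9 = 0.82 of that in the 30-day cohorts, a distortion the other way.

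The cost is SAP wording and one extra set of tables. Onset dates are already recorded (Protocol 9.2.1.1), and the Day 30 visit may run up to 3 days late but not early (Protocol 7.2), so subjects who attend on schedule cover the window. No visit, collection period or clinical rule changes.

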6.1 Safety Analysis Set

The safety set will consist of all study subjects who receive at least one dose of AMG 529 or placebo.

6.2 Pharmacokinetic Analyses Set

The PK analysis set will consist of all subjects for whom at least one PK parameter or endpoint can be reliably estimated.

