Cmax and AUC-based safety margin determinations were the basis for the second approach ([Table 1](#) and [Figure 1](#)). The NOAEL Cmax and AUC are 479000-fold and 113000-fold higher than the predicted human Cmax and AUC at the proposed starting dose of 21 mg SC in human subjects (ie, 4.59 ng/mL and 98.9 ng•day/mL). The anticipated maximum dose in the clinic, 700 mg SC, is expected to result in a Cmax and AUC that are 5490-fold and 2060-fold lower, respectively, than those observed at the NOAEL dose in the 14-day GLP toxicology study, and is intended to provide adequate safety information supporting subsequent clinical development.

**Table 1. Predicted AMG 529 Human Exposures After a Single Dose Administration for the Proposed Clinical Doses and Margins Relative to Repeat-dose Cynomolgus Monkey Exposure at the NOAEL**

[figure not shown]
Clinical Dose (mg)	Predicted Human Exposure a		Exposure Margins b	
	C max (ng/mL)	AUC 0-inf (ng•day/mL)	C max	AUC 0-7d
21 SC	4.59	98.9	479000	113000
70 SC	16.0	337	138000	33200
210 SC	55.5	1090	39600	10300
420 SC	145	2510	15200	4460
700 SC	401	5450	5490	2060
70 IV	19400	468	113	23900

a Human exposures are the predicted human exposures assuming a single dose

b Cmax of 2200 µg/mL and AUC0-7d of 11200 µg•day/mL at NOAEL (100 mg/kg SC) divided by predicted human exposure.

NOAEL= no observed adverse effect level; SC = subcutaneous; IV = intravenous; Cmax = maximum observed concentration; AUC0-inf = area under the concentration-time curve from time 0 to infinity; AUC0-7d = area under the concentration-time curve from time 0 to 7 days after the 2nd dose

**Figure 1. Predicted AMG 529 Concentration-time Profiles in Humans Following Single SC or IV Dose Administration of AMG 529**

[figure not shown]

The third approach followed a 'Minimal Anticipated Biologic Effect Level' (MABEL) paradigm ([EMA/CHMP/SWP/28367/07, Guideline on Strategies to Identify and Mitigate Risks for First-in-Human Clinical Trials with Investigational Medicinal Products](#)).

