### **10.5.3 Secondary Endpoints**

#### **10.5.3.1 Pharmacokinetics Analysis**

Serum samples will be analyzed for AMG 529 concentrations using a validated assay. Individual concentration-time plots for AMG 529 will be presented for each subject as well as mean concentration-time plots for each cohort. Pharmacokinetic parameters including but not limited to AUC,  $C_{\max}$ , and  $t_{\max}$  will be estimated using non-compartmental methods. Actual dosing and sampling times will be used for calculation of PK parameters.

Summary statistics will be generated for each PK parameter for each dose cohort. A population PK analysis may also be performed to obtain additional PK parameters.

Bioavailability may also be calculated and summarized if data collected is deemed adequate.

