8.3 Handling of Missing and Incomplete Data

The following imputation of missing values will be done:

- Incomplete adverse event and concomitant medication dates will be imputed as per [Appendix A](#). If imputed dates are used, then they will be identified as such in the final study report.
- Laboratory measurements that are below the quantification limits will be considered equal to the lower limit of quantification for all analyses unless explicitly noted otherwise.
- Biomarker data that are below the quantification limits will be considered equal to half of the lower limit of quantification for all analyses unless specified otherwise.
- PK concentrations that are below the quantification limits will be set to zero when engaging non-compartmental model to compute PK parameters.

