9.7 Other Analyses

9.7.1 Analyses of Pharmacokinetic or Pharmacokinetic/Pharmacodynamic Endpoints

9.7.1.1 Analysis of Pharmacokinetic Endpoints

The Clinical Pharmacology Modeling and Simulation (CPMS) group at Amgen will perform this part of the analysis.

Serum samples will be analyzed for AMG 529 concentrations using a validated assay. Individual concentration-time plots for AMG 529 will be presented for each subject as well as mean concentration-time plots for each cohort. Pharmacokinetic parameters including but not limited to AUC, C_{\max} , and t_{\max} will be estimated using non-compartmental methods. Actual dosing and sampling times will be used for calculation of PK parameters.

Summary statistics will be generated for each PK parameter for each dose cohort. A population PK analysis may also be performed to obtain additional PK parameters. Bioavailability may also be calculated and summarized if data collected is deemed adequate.

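### The PK set is selected on measured exposure and below-limit values become zero, so the 21 mg SC summary is biased, in a direction the text leaves open, if the assay limit is about 3 ng/mL or higher

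*SAP*

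**What the plan says.** SAP 6.2 and protocol 10.1.2.2 use the same sentence: "The PK analysis set will consist of all subjects for whom at least one PK parameter or endpoint can be reliably estimated". Neither defines what makes an estimate reliable. The safety set (SAP 6.1) depends on dosing alone. The PD set (SAP 6.3) depends on dosing and on measurements being available, not on their values.

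SAP 8.3 adds: "PK concentrations that are below the quantification limits will be set to zero when engaging non-compartmental model to compute PK parameters". It does not distinguish samples before the first quantifiable value, between quantifiable values, or after the last one.

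Protocol 10.5.3.1 then says: "Summary statistics will be generated for each PK parameter for each dose cohort". On the assay, SAP 9.7.1.1 says only: "Serum samples will be analyzed for AMG 529 concentrations using a validated assay". No quantification limit appears in either document.

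Protocol 2.5, Table 1, predicts Cmax of 4.59 ng/mL and AUC of 98.9 ng•day/mL at 21 mg SC, and Cmax of 16.0 ng/mL at 70 mg SC. Each cohort has six subjects on AMG 529.

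**The concern.** A dosed subject whose samples all fall below the limit may have no reliably estimated parameter. Such a subject can leave the PK set because exposure was low, while a cohort-mate with higher exposure stays. Alternatively, SAP 8.3 can be read as giving that subject a Cmax and AUC of zero, which keeps the subject in. These readings move the cohort mean in opposite directions, and the choice would be made after the concentrations are known.

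Separately, a subject with some quantifiable samples stays in the set, but zeros replace real low concentrations. That lowers AUC relative to what the true concentrations at the same times would give.

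Cmax and AUC are secondary endpoints (protocol 10.1.1.2). They may serve as the exposure measure in the exploratory exposure-ALP endpoint, and the PK profile is meant to inform dose and frequency in later multi-dose trials (protocol 2.6). With six active subjects per cohort, losing or zeroing one or two changes the summary visibly.

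**Working it through.** **1. The plan's own figures.** Table 1's margins are the exposure "at NOAEL (100 mg/kg SC) divided by predicted human exposure". For 21 mg SC: Cmax 2200 µg/mL = 2,200,000 ng/mL, and 2,200,000 / 4.59 = 479,303 (stated 479000). AUC: 11,200,000 / 98.9 = 113,246 (stated 113000). The 4.59 is model output, so only its consistency with the margin can be checked. It is consistent.

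**2. Assumptions for Cmax.** The documents give neither the limit L nor the between-subject CV. I take Cmax as lognormal with median m equal to the Table 1 prediction, CV 30-100% and L from 1 to 10 ng/mL. A subject is wholly below the limit when Cmax < L.

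**3. Formulas.** σ = √ln(1 + CV²) and z = ln(L/m)/σ.
- Probability that a subject is wholly below the limit: Φ(z).
- Expected mean / true mean, such subjects dropped: Φ(σ − z) / [1 − Φ(z)].
- Expected mean / true mean, such subjects kept at zero: Φ(σ − z).

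**4. Worked case: 21 mg SC, L = 4.59.** Here z = 0, so half the cohort (3 of 6) is expected to be wholly below the limit.
- CV 30%: σ = 0.294, Φ(0.294) = 0.615. Dropped 0.615/0.5 = 1.23; zero 0.62.
- CV 50%: σ = 0.472, Φ(0.472) = 0.682. Dropped 1.36; zero 0.68.
- CV 100%: σ = 0.833, Φ(0.833) = 0.797. Dropped 1.59; zero 0.80.

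**5. 21 mg SC across limits** (each range runs from CV 30% to CV 100%):

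| Assumed limit, ng/mL | Expected wholly below limit, of 6 | Mean ratio if dropped | Mean ratio if kept at zero |
|---|---|---|---|
| 1 | 0.0-0.2 | 1.00-1.03 | 1.00 |
| 2 | 0.0-1.0 | 1.00-1.15 | 1.00-0.97 |
| 3 | 0.4-1.8 | 1.04-1.31 | 0.96-0.91 |
| 4.59 | 3.0 | 1.23-1.59 | 0.62-0.80 |
| 10 | 6.0-5.0 | 2.29-2.63 | 0.01-0.46 |

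**6. 70 mg SC (m = 16.0).** If such subjects are dropped, the ratio is at most 1.06 for limits up to 4.59, and 1.03-1.29 at a limit of 10.

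**7. AUC in retained subjects.** As an illustration, I use a one-compartment curve with first-order absorption matched to Cmax 4.59 and AUC 98.9. Half-life is 7 or 10 days (the range anticipated in protocol 2.5), with the Table 4 SC sampling times, the linear trapezoid to day 30, and below-limit values set to zero. Ratios to the same trapezoid without a limit:
- Limit 1: 1.00 for both half-lives.
- Limit 2: 80.7/86.5 = 0.93 (7 days); 61.6/82.6 = 0.75 (10 days).
- Limit 3: 60.7/86.5 = 0.70; 60.2/82.6 = 0.73.
- Limit 4: 35.4/86.5 = 0.41; 34.5/82.6 = 0.42.

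**The case against.** A reader might infer that the low-dose summaries are simply biased upward. The documents do not support that. No sentence says a wholly below-limit subject is excluded, and SAP 8.3 can be read as assigning such a subject zero, which biases Cmax downward. For AUC, the zero rule pulls retained subjects down, so a net upward bias has not been shown. Exclusion is arguably the more natural reading, since a Cmax of zero from samples that are all below the limit is hardly a reliable estimate, but that remains a reading.

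The rest of the case for leaving the text alone is also substantial:
- The effect depends on an unstated limit and is negligible for an assay reading to 1 ng/mL or lower. The predicted IV peak of 19,400 ng/mL says nothing about the lower limit.
- Exclusion is narrow. One estimable parameter is enough, and Table 4 schedules 12 post-dose SC samples, any one of which could supply Cmax and tmax.
- At a limit of 10 ng/mL the large ratios describe at most about one retained subject of six, so nobody would rely on that mean.
- Exclusions would be visible. SAP 9.2 calls for a listing and summary of analysis-set inclusion, SAP 9.7.1.1 shows individual profiles, and SAP 9.1 already includes medians and ranges.
- The consequences are bounded. No dose-proportionality analysis is planned, the exposure-ALP endpoint may use dose, the ALP model in SAP 9.7.1.2 uses treatment group, and protocol 2.5 expects little or no ALP change at 21 mg.

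All of this limits the size and reach of the point. It does not settle which rule applies to a wholly below-limit subject, and it does not justify zeros after the first quantifiable value.

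**Conclusion.** The point holds in a conditional form. The set is selected on the measured outcome, the zero rule ignores position in the profile, and together they leave wholly below-limit subjects undefined. If the limit is roughly 3 ng/mL or higher, the 21 mg SC summary is biased. At an assumed limit of 4.59 ng/mL, mean Cmax is overstated by 23-59% or understated by 20-38%, depending on a choice the text does not make. AUC in a typical retained 21 mg subject is understated under either choice, by about 27-30% at a limit of 3 ng/mL.

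At 1 ng/mL the Cmax effect is at most 3%. The problem is mainly confined to 21 mg; 70 mg SC needs a limit of about 10 ng/mL or more. These sizes rest on assumed limits, an assumed CV of 30-100%, a lognormal Cmax centred on the Table 1 prediction and, for AUC, a simple illustrative curve. It is worth correcting because the correction is cheap, not because serious bias has been demonstrated.

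**What to change.** 1. In protocol 10.1.2.2 and SAP 6.2, define the PK analysis set as all subjects who received AMG 529 and have at least one post-dose PK sample assayed, quantifiable or not.
2. State the LLOQ and report the number of below-limit samples by cohort and time point.
3. Report Cmax for wholly below-limit subjects as below LLOQ, and summarise affected cohorts with medians and ranges.
4. In SAP 8.3, apply zero only to samples before the first quantifiable value, and treat later below-limit values as missing.

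Step 4 does not recover exposure below the limit. In the 7-day illustration at a limit of 3 ng/mL, AUC with zeros is 60.7, of which 7 days × 3.69 / 2 = 12.9 is an assumed fall to zero between the day 15 and day 22 samples. Without it, AUC to the last quantifiable sample is 60.7 − 12.9 = 47.8. The gain is a quantity with a known end point, so AUC should be labelled as ending at the last quantifiable sample, with that time listed.

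The cost is wording in both documents and minor PK programming, with no new samples. The downside is that some low-dose summaries may appear as below LLOQ and look less precise. If the assay proves sensitive, almost nothing changes.
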